#### **Part 2: Randomized Part**

Following the study enrollment halt during Part 1, Part 2 will not be initiated.

The primary objective is to evaluate whether spartalizumab in addition to capmatinib prolongs progression free survival (PFS) by BIRC according to RECIST 1.1 (see [Appendix 1](#)) compared to capmatinib plus placebo. The analysis will be performed on the FAS.

## 12.4.1.1 Definition of primary endpoint(s) / estimand(s)

### Overall response rate (ORR)

ORR is defined as the proportion of subjects with a confirmed best overall response (BOR) of complete response (CR) and partial response (PR) as per investigator assessment according to RECIST 1.1 (see [Appendix 1](#)).

### Progression free survival (PFS)

PFS is defined as the time from the date of randomization to the date of the first documented progression according to RECIST 1.1, or death due to any cause. Clinical deterioration without objective radiological evidence will not be considered as documented disease progression. PFS will be assessed by BIRC according to RECIST 1.1. Censoring conventions (i.e. handling of missing values/censoring/discontinuations) are provided in [Section 12.4.1.4](#).

## 12.4.1.2 Statistical hypothesis, model, and method of analysis

### Part 1: Single Arm Run-in Part

ORR as per investigator assessment calculated based on the data from the FAS and the corresponding 95% confidence intervals based on the exact binomial distribution ([Clopper and Pearson 1934](#)) will be presented.

Participants who had never received one of the investigational drugs will be excluded from the efficacy analysis.

### Part 2: Randomized Part

Following the study enrollment halt during Part 1, Part 2 will not be initiated.

The primary efficacy analysis to test these hypotheses and compare the two treatment groups will be based on a stratified log-rank test at an overall one-sided 2.5% significance level. The following null and alternative hypothesis will be tested to address the primary efficacy objective for PFS based on BIRC as per RECIST 1.1:

$$H_0: \theta_1 \geq 1 \text{ vs } H_1: \theta_1 < 1$$

Where  $\theta_1$  is the PFS hazard ratio (HR) (capmatinib in combination with spartalizumab versus capmatinib plus placebo). The stratification will be based on the stratification factors assigned at randomization (i.e. presence or absence of brain metastasis at baseline [as assessed investigator per RECIST 1.1] and PD-L1 expression [ $<1\%$ , or  $1-49\%$ , or  $\geq50\%$ ]).

The PFS will be analyzed at the interim analysis and final analysis of a group sequential design, using a Lan-DeMets ([O'Brien and Fleming 1979](#)) alpha spending function.

PFS will be summarized using the Kaplan-Meier (KM) method, based on FAS. Median PFS, with corresponding 95% CI, and 25th and 75th percentiles (Brookmeyer and Crowley 1982, Klein and Moeschberger 1997) will be presented by treatment group. KM estimates for PFS proportions at specific timepoints, along with 95% CI (Greenwood's formula, Kalbfleisch and Prentice 2002) will also be provided. The hazard ratio for PFS will be estimated, along with its 95% confidence interval, using a stratified Cox proportional hazard model using the same stratification factors as for the log-rank test. If there are too few patients/events in a given stratum, strata might be grouped for the analysis. Further details will be provided in the SAP.

### **If PFS is not statistically significant at the PFS interim analysis:**

PFS data will be tested at the time of the final PFS analysis.

### **If PFS is statistically significant at the PFS interim analysis:**

The subsequent PFS analysis will still be performed to obtain more PFS data and additional follow-up PFS analyses may also be performed earlier than planned primary PFS analysis at the request of Health Authorities or to facilitate health authority interactions. Note that in this case, the PFS analysis will only be descriptive and no statistical testing will be performed for the analysis.

#### **12.4.1.3 Handling of intercurrent events of primary estimand**

##### **Part 1: Single Arm run-in Part**

The primary estimand will account for the different intercurrent events as follows:

- **Discontinuation of spartalizumab for any reason:** BOR will take into account all available tumor assessments irrespective of spartalizumab discontinuation reasons.
- **Discontinuation of tumor assessment follow up with approval of protocol amendment:** BOR will take into account all available tumor assessments up to the last valid tumor assessment prior to approval of protocol amendment.
- **Any public health emergency as declared by local or regional authorities, e.g., pandemic, epidemic or natural disaster:** BOR will take into account all tumor assessments irrespective of any public health emergency.
- **New anti-neoplastic therapy:** Tumor assessment data collected after starting new anti-neoplastic therapy will be excluded from the BOR derivation.

##### **Part 2: Randomized Part**

Following the study enrollment halt during Part 1, Part 2 will not be initiated.

The primary estimand will account for the different intercurrent events as follows:

- **Discontinuation of study treatment for any reason before radiological progression or death due to any cause:** tumor assessment data collected after discontinuation of study treatment (or spartalizumab only) will be used for PFS
- **New anti-cancer therapy before radiological progression or death due to any cause:** PFS events documented after the start of new anti-cancer therapy will be used to derive the time to event for the primary analysis

- **Radiological progression or death observed after 2 or more missing tumor assessments:** radiological progression or death observed after 2 or more missing tumor assessments will not be included in the derivation of the time to event for PFS, and the observation will be censored at the time of the last adequate tumor assessment prior to the first missing assessment
- **Lack of post-baseline tumor assessment:** Subjects without a post-baseline tumor assessment will be censored at the time of the randomization

#### **12.4.1.4 Handling of missing values/censoring/discontinuations**

##### **Part 1: Single Arm Run-in Part**

Subjects in the FAS with unknown best overall response (BOR) will be noted as such in the appropriate tables/listings and counted as non-responders in the ORR calculation.

If there is no baseline tumor assessment, all post-baseline overall lesion responses are expected to be ‘Unknown’. If no valid post-baseline tumor assessments are available, the best overall response must be “Unknown” unless progression or death is reported.

If any new anti-neoplastic therapy is taken while on study any subsequent assessments would be excluded from the BOR derivation.

Subjects without confirmed CR/PR, due to lack of subsequent tumor assessment after one CR/PR, will be considered as non-responders.

##### **Part 2: Randomized Part**

Following the study enrollment halt during Part 1, Part 2 will not be initiated.

In the primary PFS analysis, PFS will be censored at the last adequate tumor assessment if no PFS event is observed prior to the cut-off date.

#### **12.4.1.5 Sensitivity and supplementary analyses**

##### **Part 1: Single Arm Run-in Part**

A sensitivity analysis may be performed where subjects without a valid post-baseline assessment (unless PD or death is reported before that time) are excluded from the calculation of the ORR.

##### **Part 2: Randomized Part**

Following the study enrollment halt during Part 1, Part 2 will not be initiated.

##### **Sensitivity Analyses**

As a sensitivity analysis, PFS as per investigator assessment will be analyzed using a stratified Cox proportional hazard model, with the same analysis convention as for the primary analysis. The treatment effect will be summarized by the hazard ratio with its 95% confidence interval. Kaplan-Meier curves, medians and 95% confidence intervals of these medians will be presented for each treatment group.

## Supplementary Analyses

As supplementary analyses performed in the FAS, the hazard ratio and 95% confidence interval for PFS per BIRC review will be obtained from:

1. an unstratified and covariate unadjusted Cox model.
2. a stratified and covariate adjusted Cox model including as covariates the following: gender, age groups (<65,  $\geq$ 65 years), ECOG PS (0, 1), histology (squamous, non-squamous), smoking status (smoker, non-smokers, ex-smokers), race (Asian, other). A list of covariates will be defined in the SAP.
3. If the primary analysis of PFS is statistically significant, sub group analysis to assess the homogeneity of the treatment effect across demographics and baseline characteristics will be performed. The following subgroups may be considered: gender, age groups (<65,  $\geq$ 65 years), ECOG PS (0, 1), histology (squamous, non-squamous), smoking status (smoker, non-smokers, ex-smokers), race (Asian, other), presence or absence of brain metastasis at baseline (as assessed investigator per RECIST 1.1) and PD-L1 expression (<1%, or 1-49%, or  $\geq$ 50%). A final list of subgroups of interest will be defined in the SAP.

Additional key supplementary analysis will be performed to take into account the possible delayed immunotherapy response (e.g. weighted log-rank test with Fleming-Harrington class of weights) and to assess the robustness of the primary analysis results for PFS. A weighted log-rank test using Fleming-Harrington class of weights will be used. Such analyses will be detailed in the SAP.

If proportional hazard assumption is violated as a result of a delayed treatment effect, a stratified piecewise Cox regression analysis will be performed based on PFS to estimate a hazard ratio within pre-specified time periods (0-3 months and  $>$ 3 months, based on an assumed 3 months delay effect for PFS). The analysis will be performed by incorporating a time-dependent covariate into the model and estimating the treatment effect for each of the two time periods. The hazard ratio, 95% CIs and Wald P-value will be provided for each time period.

## 12.5 Analysis of secondary endpoints / estimands

### 12.5.1 Key secondary endpoint (Part 2: Randomized Part)

Following the study enrollment halt during Part 1, Part 2 will not be initiated. Therefore, analysis and statistical methods for Part 2 are not applicable.

The key secondary objective is to evaluate whether spartalizumab when added to capmatinib prolongs OS compared to capmatinib plus placebo. The analysis will be performed on the FAS.

OS is defined as the time from the date of randomization to the date of death due to any cause. If the subject is alive at the date of the analysis cut-off or lost to follow-up, then OS will be censored at the last contact date prior to data cut-off date.

The following null and alternative hypothesis will be tested to address the key secondary objective for OS:

$$H_{02}: \theta_2 \geq 1 \text{ vs } H_{12}: \theta_2 < 1$$

Where  $\theta_2$  is the OS hazard ratio (capmatinib in combination with spartalizumab versus capmatinib plus placebo). The key secondary analysis to test these hypotheses and compare the two treatment groups will consist of the stratified log-rank test at an overall one-sided 2.5% significance level. The stratification will be based on the stratification factors assigned at randomization (i.e. presence or absence of brain metastasis (as assessed by investigator per RECIST 1.1) and PD-L1 expression [ $<1\%$ , or  $1\text{-}49\%$ , or  $\geq 50\%$ ]).

A maximum of four analyses are planned for OS. OS will be hierarchically tested in the following way:

1. at the time of the interim analysis for PFS when approximately 49% (96 deaths) are expected to occur. If PFS is statistically significant at this stage, OS will also be tested. If PFS is not statistically significant at this stage, then OS will not be tested. Note that if OS is not tested a conservative approach is used where some alpha, corresponding to the information fraction of OS events available at that time, will be spent.
2. at the time of the final analysis for PFS when approximately 75% (146 deaths) are expected to occur. If PFS is statistically significant at this stage, OS will also be tested. If PFS is not statistically significant at this stage, then OS will not be tested.
3. When approximately 85% of the deaths have been observed (167 deaths) in case the time gap between the final analyses for PFS and for OS is longer than 1 year. If PFS is not statistically significant, at the interim or the primary analysis, OS will not be tested.
4. at the final OS analysis of a group sequential design. If PFS is not statistically significant, at the interim or the primary analysis, OS will not be tested.

The type I error will be controlled using a Lan-DeMets (O'Brien and Fleming 1979) alpha spending function for OS which is independent of the one used for PFS. This guarantees the protection of the overall type I error ( $\alpha = 2.5\%$ ) across all hypotheses and the repeated testing of the OS hypotheses at the interim and the final analyses (Glimm et al 2010).

OS will be summarized using the KM method, based on FAS. Median OS, with corresponding 95% CI, and 25th and 75th percentiles (Brookmeyer and Crowley 1982, Klein and Moeschberger 1997) will be presented by treatment group. KM estimates for OS proportions at specific timepoints, along with 95% CI (Greenwood's formula, Kalbfleisch and Prentice 2002) will also be provided. The hazard ratio for OS will be estimated, along with its 95% confidence interval, using a stratified Cox proportional hazard model using the same stratification factors as for the log-rank test. If there are too few patients/events in a given stratum, strata might be grouped for the analysis. Further details will be provided in the SAP.

## 12.5.1.1 Handling of intercurrent events of key secondary estimand

The key secondary estimand will account for the different intercurrent events as follows:

- **Discontinuation of study for any reason:** OS will be analyzed based on the survival follow-up irrespective of the study discontinuation. OS will be censored at the last contact date if the subject discontinued from study due to lost to follow-up or withdrew consent or did not continue to the survival follow up phase.
- **New anti-cancer therapy:** OS will be analyzed regardless of whether new anti-neoplastic therapy is initiated. Death collected after the start of new anti-cancer therapy will be used for OS analysis.

## 12.5.1.2 Sensitivity and supplementary analyses

If the OS analysis (either interim or final) is statistically significant, supplementary analyses will be performed in the FAS, the hazard ratio and 95% confidence interval for OS will be obtained from:

- an unstratified and covariate unadjusted Cox model.
- a stratified and covariate adjusted Cox model including as covariates the following: gender, age groups ( $<65$ ,  $\geq 65$  years), ECOG PS (0, 1), histology (squamous, non-squamous), smoking status (smoker, non-smokers, ex-smokers), race (Asian, other). A final list of covariates will be defined in the SAP.
- a sub group analysis to assess the homogeneity of the treatment effect across demographics and baseline characteristics will be performed. The following subgroups maybe considered: gender, age groups ( $<65$ ,  $\geq 65$  years), ECOG PS (0, 1), histology (squamous, non-squamous), smoking status (smoker, non-smokers, ex-smokers), race (Asian, other), presence or absence of brain metastasis at baseline (as assessed investigator per RECIST 1.1) and PD-L1 expression ( $<1\%$ , or 1-49%, or  $\geq 50\%$ ). A final list of subgroups of interest will be defined in the SAP.

## 12.5.2 Other secondary endpoint(s)

### 12.5.2.1 Efficacy endpoint(s)

#### Part 1: Single Arm Run-in Part

The secondary efficacy endpoints are the following:

- Disease control rate (DCR) and progression free survival (PFS) by investigator assessment as per RECIST 1.1.

#### Part 2: Randomized Part

Following the study enrollment halt during Part 1, Part 2 will not be initiated. Therefore, the analysis for Part 2 are not applicable.

The secondary efficacy endpoints are the following:

- Progression free survival (PFS) by investigator assessment as per RECIST 1.1.

- Disease control rate (DCR), duration of response (DOR), overall response rate (ORR) and time to response (TTR) by investigator assessment and BIRC as per RECIST 1.1.

## Disease control rate (DCR)

DCR is defined as the proportion of subjects with a confirmed best overall response (BOR) of complete response (CR), partial response (PR) and stable disease (SD) according to RECIST 1.1 (see [Appendix 1](#)).

DCR calculated based on the data from the FAS and the corresponding 95% confidence intervals based on the exact binomial distribution ([Clopper and Pearson 1934](#)) will be presented.

Participants who had never received one of the investigational drugs will be excluded from the DCR analysis.

## Progression free survival (PFS)

The analysis in this section refer to the PFS as per local investigator assessment for Part 1.

PFS is defined as the time from the date of start of treatment (Part 1) to the date of the first documented progression according to RECIST 1.1, or death due to any cause. If a subject has no progression or death, the subject is censored at the date of last adequate tumor assessment. Definition of last adequate tumor assessment is provided in [Appendix 1](#).

PFS will be summarized using the KM method, based on FAS. Median PFS, with corresponding 95% CI, and 25th and 75th percentiles ([Brookmeyer and Crowley 1982](#), [Klein and Moeschberger 1997](#)) will be presented. KM estimates for PFS proportions at specific timepoints, along with 95% CI ([Greenwood's formula](#), [Kalbfleisch and Prentice 2002](#)) will also be provided.

Participants who did not receive one of the investigational drugs will be excluded from the PFS analysis.

PFS will be censored at the date of the last adequate tumor assessment prior to the earliest of analysis cut-off date, the start of a subsequent anti-neoplastic therapy (if any), if the event occurred after two or more missing tumor assessments, or study treatment discontinuation before radiological progression or death. Clinical progression without objective radiological evidence will not be considered as documented disease progression. The date of last adequate tumor assessment is the date of the last tumor assessment with overall lesion response of CR, PR or SD before an event or a censoring reason occurred. If no post-baseline assessments are available (before an event or a censoring reason occurred), the date of enrollment will be used.

The number of subjects censored and reasons for censoring will be summarized using descriptive statistics.

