**Table 8-3 Imaging Assessment Collection Plan**

Procedure	Screening/Baseline	During Treatment/Follow-up
CT or MRI of chest, abdomen and pelvis with i.v. contrast	Mandated	Mandated every 8 weeks (+/- 7 days) until at least 2 post-baseline assessments have been obtained, then every 12 weeks thereafter until PD determined by investigator assessment (with or without confirmation by BIRC) or EOT. Following the approval of protocol amendment 01, tumor assessment follow up will not be performed and study imaging will no longer be reviewed by BIRC.
CT or MRI of brain with i.v. contrast	Mandated	Mandated if positive at baseline following the same schedule as CT/MRI of chest, abdomen, and pelvis. Or if clinically indicated.
CT or MRI of other metastatic sites (e.g., neck, etc.)	Mandated if metastatic sites are suspected	If other metastatic sites are positive at baseline, follow the same schedule as CT/MRI of chest, abdomen, and pelvis. Or if clinically indicated.
Whole body bone scan*	Mandated	If clinically indicated.
Localized bone CT, MRI or X-ray	Mandated for any lesions identified on the whole body bone scan that are not visible on the CT/MRI of chest, abdomen, and pelvis or brain	If positive at baseline follow the same schedule as CT/MRI of chest, abdomen, and pelvis. Or if clinically indicated.
Color photographs with a metric ruler	Mandated if skin metastases are present.	If positive at baseline follow the same schedule as CT/MRI of chest, abdomen, and pelvis. Or if clinically indicated.

\*Whole body bone scan according to imaging vendor specifications.

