### 8.3.1.2 Post-baseline imaging assessments

Imaging assessments as described in [Table 8-3](#) should be performed at the time points specified using the same imaging modality used at baseline, irrespective of study treatment interruption or actual dosing (see [Table 8-1b](#) or [Table 8-2](#)). Imaging assessments for response evaluation will be performed every 8 weeks (+/- 7 days) until at least 2 post-baseline imaging assessments have been acquired, then every 12 weeks thereafter until disease progression as determined by investigator assessment per RECIST 1.1 or until EOT, whichever occurs the earliest.

**Note:** Imaging assessments should be scheduled using the first dose of study treatment in Part 1 and the day of randomization for Part 2 as the reference date (not the date of the previous tumor assessment), and should be respected regardless of whether treatment with study treatment is temporarily withheld or unscheduled assessments performed.

Additional imaging assessments may be performed at any time during the study at the investigator's discretion to support the efficacy evaluations for a subject, as necessary.

Clinical suspicion of disease progression at any time requires a physical examination and imaging assessments to be performed promptly rather than waiting for the next scheduled imaging assessment.

Each lesion that is measured at baseline must be measured by the same method (either same imaging method or by photography, including a metric ruler) and when possible, by the same local radiologist/physician throughout the study so that the comparison is consistent. If an off-schedule imaging assessment is performed because progression is suspected, subsequent imaging assessments should be performed in accordance with the original imaging schedule.

Combined PET/CT may be used only if the CT is of similar diagnostic quality as a CT performed without PET, including the utilization of *iv* contrast media. At the discretion of the Investigators, FDG-PET scans may be performed to document disease progression per RECIST 1.1 ([Appendix 1](#)).

All complete responses (CRs) and partial responses (PRs) must be confirmed by a second assessment. If the second assessment is performed outside the normal window of scans, it should not be performed earlier than 4 weeks after the scan where the criteria for response were first met.

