Situations C (C1 and C2): Progression or death after one or more missing assessments: The primary analysis is usually using options (1) for situations C1 and C2, i.e.

- (C1) taking the actual progression or death date, in the case of only one missing assessment.
- (C2) censoring at the date of the last adequate assessment, in the case of two or more consecutive missing assessments.

In the case of two or missing assessments (situation C2), option (3) may be considered jointly with option (1) in situation C1 as sensitivity analysis. A variant of this sensitivity analysis consists of backdating the date of event to the next scheduled assessment as proposed with option (2) in situations C1 and C2.

**Situation E: Treatment discontinuation due to 'Disease progression' without documented progression:** By default, option (1) is used for situation E as patients without documented PD should be followed for progression after discontinuation of treatment. However, option (2) may be used as sensitivity analysis. If progression is claimed based on clinical deterioration instead of tumor assessment by e.g. CT-scan, option (2) may be used for indications with high early progression rate or difficulties to assess the tumor due to clinical deterioration.

**Situation F: New cancer therapy given:** the handling of this situation must be specified in detail in the protocol. However, option (1) (ITT) is the recommended approach; events documented after the initiation of new cancer therapy will be considered for the primary analysis i.e. progressions and deaths documented after the initiation of new cancer therapy would be included as events. This will require continued follow-up for progression after the start of the new cancer therapy. In such cases, it is recommended that an additional sensitivity analysis be performed by censoring at last adequate assessment prior to initiation of new cancer therapy.

Option (2), i.e. censoring at last adequate assessment may be used as a sensitivity analysis. If a high censoring rate due to start of new cancer therapy is expected, a window of approximately 8 weeks performed after the start of new cancer therapy can be used to calculate the date of the event or censoring. This should be clearly specified in the analysis plan.

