#### **Progression free survival (PFS)**

PFS is defined as the time from the date of start of treatment to the date of the first documented progression according to RECIST 1.1, or death due to any cause. Clinical deterioration without objective radiological evidence will not be considered as documented disease progression.

PFS will be summarized using the KM method, based on FAS. Median PFS, with corresponding 95% CI, and 25th and 75th percentiles ([Brookmeyer and Crowley 1982](#), [Klein and Moeschberger 1997](#)) will be presented. KM estimates for PFS proportions at specific timepoints (3, 6, 9, 12, and 18

months), along with 95% CI (Greenwood's formula, [Kalbfleisch and Prentice 2002](#)) will also be provided. The number (%) of events and subjects censored will also be summarized.

Participants who had never received one of the investigational drugs will be excluded from the PFS analysis.

PFS will be censored at the date of the last adequate tumor assessment prior to the earliest of analysis cut-off date, the start of a subsequent anti-neoplastic therapy (if any), if the event occurred after two or more missing tumor assessments, or study treatment discontinuation before radiological progression or death (for patients who discontinued study treatment before radiological progression/death and also prior to the approval of protocol version 01, PFS will be censored at the date of the last adequate tumor assessment prior to the approval of protocol version 01). The date of last adequate tumor assessment is the date of the last tumor assessment with overall lesion response of CR, PR or SD before an event or a censoring reason occurred. If no post-baseline assessments are available (before an event or a censoring reason occurred), the date of enrollment will be used. If a subject has no progression or death, the subject is censored at the date of last adequate tumor assessment.

The number of subjects censored and reasons for censoring will be summarized using descriptive statistics.

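### After amendment 01, Part 1 PFS can be overstated: a subject who stops treatment for clinical progression without RECIST PD is censored, and no PFS sensitivity analysis covers this

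*Protocol*

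**What the plan says.** Protocol section 12.5.2.1 (Part 1 PFS, investigator assessment) has two rules that act together. The first is "Clinical progression without objective radiological evidence will not be considered as documented disease progression"; SAP section 2.7.1 has the equivalent, "Clinical deterioration without objective radiological evidence will not be considered as documented disease progression". The second lists, among the reasons to censor at the last adequate scan, "study treatment discontinuation before radiological progression or death".

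Appendix 1, section 16.1.3.2.10, treats treatment stopped for progression without documented PD as situation E. Option (1) ignores the clinical progression. Option (2) counts an event at the discontinuation date. The reason for the default is given: "By default, option (1) is used for situation E as patients without documented PD should be followed for progression after discontinuation of treatment". The alternative follows: "However, option (2) may be used as sensitivity analysis".

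Table 8-3 says that after approval of amendment 01 "tumor assessment follow up will not be performed", and section 8.3.1.2 runs imaging "until disease progression as determined by investigator assessment per RECIST 1.1 or until EOT, whichever occurs the earliest".

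SAP section 2.7.1 adds an exception that the protocol lacks. Subjects who stopped treatment before progression and before approval of the amended protocol are censored at their last adequate scan before that approval, not at treatment stop.

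**The concern.** The default for situation E is harmless while scans continue after treatment stops, because the progression is then picked up at a later scan. Once scans end with treatment, it is not picked up. A subject who comes off treatment with symptomatic progression, and has no scan showing RECIST PD, is censored at the previous adequate scan, up to about 12 weeks earlier. Censoring then coincides with failure and is informative, and the bias in the Kaplan-Meier curve is upward.

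Appendix 1 asks that the protocol and analysis plan describe one or more sensitivity analyses for event and censoring dates. The only sensitivity analysis planned for Part 1 is for ORR (protocol 12.4.1.5, SAP 2.5.5). At stake are the PFS median and the 3-, 6-, 9-, 12- and 18-month rates listed in SAP 2.7.1.

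**Working it through.** **Plan figure.** The documents give no Part 1 PFS target, event count or power, so there is no PFS figure to reproduce.

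**Who is exposed.** The Study Update in Amendment 1 gives 28 subjects on the combination and 3 who started capmatinib alone: 28 + 3 = 31 treated. The 3 are excluded from PFS, leaving 28. On 06-Sep-2021, 19 were still on treatment, so 31 − 19 = 12 were off. Depending on where the 3 fall, 19 − 3 = 16 to 19 of the 28 were still on treatment, and 12 − 3 = 9 to 12 were off. Those who stop after approval do not have the SAP exception.

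**Size: inputs.**
- Median PFS 9.69 months, capmatinib alone in first line (protocol 1.1.1.2), used for illustration and taken as exponential: λ = ln 2 / 9.69 = 0.0715 per month.
- Scans at weeks 8 and 16, then every 12 weeks (8.3.1.2).
- f = share of progressions that are clinical-only. The documents give no value; a range is shown.

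**Closed form for the 12-month rate.** If clinical-only progressions are censored, the curve estimates a hazard of (1 − f)λ, so S(12) = exp(−(1 − f) × 0.0715 × 12):
- f = 0: exp(−0.858) = 42.4%
- f = 5%: exp(−0.815) = 44.2%
- f = 10%: exp(−0.773) = 46.2%
- f = 20%: exp(−0.687) = 50.3%

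**Simulation on the scan grid.** 28 subjects, 1,500 replicates, radiological progression dated at the next scan. Clinical-only cases are handled in three ways: censored at the previous scan (plan), event at the clinical date (option 2), or event at the next scan (as if follow-up had continued).

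| f | 12-month PFS, plan | Option (2) | Scans continued | Median, plan (months) | Median, option (2) (months) |
|---|---|---|---|---|---|
| 5% | 44.1% | 42.6% | 42.8% | 11.96 | 11.96 |
| 10% | 46.2% | 42.7% | 42.5% | 11.96 | 11.96 |
| 20% | 49.7% | 42.4% | 42.3% | 11.96 | 10.86 |
| 30% | 53.8% | 42.2% | 42.9% | 14.72 | 10.93 |

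The two methods agree at 12 months. With all 28 progressing, 5%, 10% and 20% are 0.05 × 28 = 1.4, 2.8 and 5.6 subjects.

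The median moves in steps because events fall on scan dates: week 52 is 52 × 7 / 30.4375 = 11.96 months and week 64 is 14.72 months.

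Between scans, option (2) dates events earlier than a scan would. At 6 months with f = 10%, the plan reads 78.8%, option (2) 75.4% and continued scans 77.2%, so part of that gap is dating rather than bias.

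**Limits.** The model applies f to every subject from the start, whereas the full mechanism applies only after approval. The exponential base is also illustrative: the reference study itself reports 49.7% at 12 months, not 42.4%. The shift matters more than the level.

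**The case against.** The other side has several good points.

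- **Not every such subject is affected.** A reader might infer that all subjects who stop for clinical progression are censored with no chance of an event. The documents do not support that. Under the SAP exception, scans between treatment stop and approval can still yield an event for those who stopped earlier. Section 8.3.1.2 also requires prompt imaging on clinical suspicion, so some cases will become radiological PD before treatment ends. Neither covers a subject who stops after approval without a qualifying scan. Appendix 1, section 16.1.4.4, in generic text, allows that such discontinuations occur and asks that they be reviewed.
- **Appendix 1 permits ending follow-up.** Section 16.1.3.2.1 allows a phase I or II study to do so if the protocol says so, and this one does. That permits the change in scanning but does not make the censoring non-informative. The Part 2 definition also ignores clinical deterioration, but section 12.4.1.3 used scans after treatment stop there, so the premise held.
- **Censoring reasons and discontinuation reasons are reported.** True, but separately. The PFS censoring categories in section 16.1.4.5.6 have none for clinical progression, and the disposition table in SAP 2.3.1 does not separate clinical from RECIST progression. The affected subjects cannot be counted from either.
- **The shift is small against the noise.** At n = 28 the standard error of a 42.4% rate is √(0.424 × 0.576 / 28) ≈ 9 points even without censoring, so shifts of 2-4 points at f = 5-10% lie inside it. This stands and limits the severity.
- **The median.** A reader might infer inflation by 1/(1 − f), for example 9.69 / 0.8 = 12.1 months. That ignores the scan schedule; on the grid with 28 subjects the planned median does not move up to f = 20%.

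**Conclusion.** The point holds as a conditional risk. For subjects who stop after approval of amendment 01 because of clinical progression without RECIST PD on a scan, the clause censoring at treatment discontinuation, together with the rule ignoring clinical progression, produces informative censoring. The reason Appendix 1 gives for that default no longer applies, and no PFS sensitivity analysis is planned.

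That PFS will be overstated does not follow from the documents: it needs at least one such subject, the number is not given, and at f = 0 there is no bias. Under the assumed 5%, 10% or 20%, 12-month PFS reads about 44%, 46% or 50% instead of about 42-43%. These figures rest on an exponential curve and on f applying to all subjects.

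Severity is minor. Part 1 PFS is a single-arm descriptive secondary endpoint with no test, threshold or sample size attached, and Part 2 will not open.

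**What to change.** Keep radiological PFS as the main analysis. In SAP 2.7.1, with a matching line in protocol 12.5.2.1:

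1. Pre-specify one supplementary Kaplan-Meier analysis using Appendix 1 situation E option (2): discontinuation for progressive disease without RECIST PD counts as an event at the discontinuation date.
2. Report the number of such subjects beside the main result, split by whether they stopped before or after approval of the amendment.
3. State that the follow-up premise for option (1) is no longer met after amendment 01.
4. Reconcile the protocol and SAP censoring text for subjects who stopped before approval. Section 4 of the SAP currently lists no change from the protocol.

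The cost is a paragraph of SAP text and one extra run. Discontinuation reasons and tumor assessments are already collected, and no visit or scan changes. Under SAP section 1 this is an amendment if made before database lock. The downside is that clinical progression is a subjective judgment in an open-label study and option (2) dates events earlier than a scan would, so the analysis should be supplementary only.
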